#### **5.11.1.1 Incidence of Adverse Events**

Overall summary tables of TEAEs will be presented showing the number and percentages of subjects with any TEAEs, any TEAEs by maximum severity, any study drug-related TEAEs, treatment-emergent SAEs, any treatment-emergent GI AE, TEAEs leading to study drug withdrawal, and TEAEs with fatal outcome.

The following TEAEs will be summarized by frequency and percentage of subjects by SOC (in alphabetical order) and PT (by decreasing frequency in the K-757 + K-833 arm):

- TEAEs
- TEAEs by maximum severity
- Study drug-related TEAEs
- Treatment-emergent SAEs
- TEAEs leading to study drug withdrawal

If the same AE (preferred term) is reported more than once for the same subject, it will be only counted once in the summary table. For the summary table by severity, if the same AE (preferred term) is reported more than once for the same subject, the maximum severity grade (severe > moderate > mild) will be counted in the summary table.

The following by-subject listings will be provided:

- AEs
- SAEs
- TEAEs leading to study drug withdrawal

#### 5.11.1.2 Gastrointestinal (GI) Adverse Event

GI relationship of each AE will be assessed during study. Number and proportion of participants experiencing any treatment-emergent GI AE, nausea, vomiting, diarrhea, constipation, during each week will be summarized by week for each treatment group, respectively. Proportion will be

calculated based on number of participants reached specified week during on-treatment period. On-treatment period for safety analyses are defined as from randomization to earlier of end of study date or last dose date +2 weeks. Days from randomization for each week will follow table below. By-week incidence of any GI AE, nausea, vomiting will also be presented by maximum severity using line graph.

Week	Days from Randomization of when experiencing AE
Week 0	1
Week 1	2 - 8
Week 2	9 - 15
Week 3	16 - 22
Week 4	23 - 29
Week 5	30 - 36
Week 6	37 - 43
Week 7	44 - 50
Week 8	51 - 57
Week 9	58 - 64
Week 10	65 - 71
Week 11	72 - 78
Week 12	79 - 85
Week 13	86 - 92
Week 14	93 - 99
Week 15	100 - 106

Time from randomization to treatment-emergent gastrointestinal adverse events (weeks) will also be analyzed. For participants who experienced any GI AE, time from randomization to any gastrointestinal adverse events is defined as duration of time from randomization to start date of first GI AEs. Participants who did not have a GI TEAEs will be censored at earlier date of end of study date or the date of last dose date + 2 weeks. The Kaplan-Meier curves will be displayed by treatment group. Same analyses will be repeated for time from randomization to treatment-emergent nausea, time from randomization to treatment-emergent vomiting, time from randomization to treatment-emergent constipation.

Time from randomization to treatment discontinuation (weeks) will also be analyzed. For participants who discontinued treatment, time to treatment discontinuation is defined as duration of time from date of randomization to the date of treatment discontinuation. Participants who complete treatment will be censored at last treatment date. The Kaplan-Meier curves will be

displayed by treatment group.

Time from randomization to treatment discontinuation due to any adverse events (weeks) will also be analyzed. For participants who discontinued treatment due to AE, time to treatment discontinuation due to AE is defined as duration of time from date of randomization to the date of treatment discontinuation. Participants who discontinue treatment due to any other reasons will be censored at the date of treatment discontinuation. Participants who complete treatment will be censored at last treatment date. The Kaplan-Meier curves will be displayed by treatment group.

Time from randomization to treatment discontinuation due to any gastrointestinal adverse events (weeks) will also be analyzed. For participants who discontinued treatment due to GI AE, time to treatment discontinuation due to GI AE is defined as duration of time from date of randomization to the date of treatment discontinuation. Participants who discontinue treatment due to any other reasons will be censored at the date of treatment discontinuation. Participants who complete treatment will be censored at last treatment date. The Kaplan-Meier curves will be displayed by treatment group.

A swimmer plot for subjects with GI AEs by preferred term and severity may be provided.

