**Table 2: Study Schedule of Assessments (Continued)**

SOA													
	Screening Period	Treatment Phase by Week											ET or Post Study F/U
Visit Number	1	2 Rand.	3	4	5	6	7 g	8	9	10	11 g	12	13
Week e	~4 Weeks	Week 0	Week 1	Week 2	Week 3	Week 4	Week 5	Week 6	Week 8	Week 10	Week 12	EoT 13	Week 15
Study Day	-28	1	8	15	22	29	36	43	57	71	85	92	105
Visit Window (days)	0	0	±2	±2	±2	±2	±3	±3	±3	±3	±3	±3	±3
Efficacy and Other Endpoint Related Assessments													
Blood for K-757/K-833 PK (trough)							X			X		X	
Blood Samples for PD (trough)		X							X			X	
Body Weight	X	X				X			X			X	X
Other													
Telephone Check g							X				X		
Optional Genetic Blood Sample h												X	

a Just prior to Randomization, it will be confirmed that no excluded/prohibited medications are being taken and, in females of child-bearing potential, that the V2/Randomization urine pregnancy test is negative.

b Urinalysis at Screening only.

c Safety labs will be collected in the fasted state except at Screening.

d Serum hCG at screening and Post-study; urine hCG at randomization and Weeks 4, and 8 for females of childbearing potential. FSH test at screening only for females of non-childbearing potential due to menopause. If screening FSH test is not consistent with menopausal status, subjects may return for a serum pregnancy test and participate under requirements for females of child-bearing potential (contraception and pregnancy testing).

e Week indicates the duration of treatment completed prior to the visit, not the week in which the visit occurs. For example, the “Week 1” visit is targeted to occur on Day 8 (the first day of the 2nd week of treatment).

f Titration will occur according to [Table 9](#). On trial site visit days when laboratory safety tests are collected, participants will fast overnight and prior to study drug administration. Dosing will end with the PM dose on Day 91.

g Telephone calls at Visits 7 and 11 (Day 85) to confirm drug compliance, assess AEs, and concomitant medications.

h The optional genetic sample may be collected at any time during the study.

Abbreviations: EoT = end of treatment; ET = end of trial; FU = follow up; hCG = human chorionic gonadotropin

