**Table 9: Dosing Table**

Arm	Time (AM/PM)		Week			
			Week 0 (D1-7)	Week 1 (D8-14)	Week 2 (D15-21)	Week 3 through 13 (D22-92)
K-757+K-833	AM	757/833 (mg)	30/100	30/100	60/100	120/100
	PM	757/833 (mg)	pbo/pbo	30/100	60/100	120/100
K-757 alone	AM	757/833 (mg)	30/pbo	30/pbo	60/pbo	120/pbo
	PM	757/833 (mg)	pbo/pbo	30/pbo	60/pbo	120/pbo
Placebo to K-757 and K-833	AM	757/833 (mg)	pbo/pbo	pbo/pbo	pbo/pbo	pbo/pbo
	PM	757/833 (mg)	pbo/pbo	pbo/pbo	pbo/pbo	pbo/pbo

Refer to Section 5.4.1 for additional titration information.

Participants will return to the trial site at the times described in the schedule of assessments (SOA) (Table 2) to complete study procedures. During two of the on-treatment weeks when participants do not return to the trial site, the site will contact the participants by phone in order to assess study medication compliance, new concomitant medication use, and AEs.

Starting at the randomization visit (Visit 2), all participants will receive nutritional and physical activity counseling from a dietician or similarly qualified healthcare professional designated by primary investigator see Section 11.1. This counseling will occur at select visits according to the SOA (Table 2).

Safety and tolerability will be assessed in an ongoing fashion through physical examination, vital sign assessment, 12-lead electrocardiogram (ECG), clinical laboratory assessments, and collection of serious and non-serious adverse events (AEs). Specific time points are described in Table 2.

Plasma will be obtained for PK and PD at select time points during treatment (Table 2).

To mitigate mechanism-related GI intolerance, K-757 and K-833 will be titrated according to Table 9. In the combination arm and the K-757-only arm, K-757 will be titrated to the maintenance dose of 120 mg BID by Day 22. K-833 will be initiated at 100 mg QAM and will be titrated to the maintenance dose of 100 mg BID on Day 8.

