#### 3 Study Design

#### 3.1 Overall Study Design

This is a randomized, double-blind, placebo-controlled 13-week study to evaluate the efficacy of K-757 alone and in combination with K-833 versus placebo in participants who are obese without type 2 diabetes mellitus (T2DM). Approximately 150 participants will be enrolled and randomized 1:1:1 to receive K-757 alone, K-757 + K-733, or matching placebos (Figure 1 and Table 1)

Figure 1: Study Schematic

<sup>a Screening will occur over approximately 4 weeks.

The study will be comprised of a Screening period (up to 28 days prior to the treatment period), a 13-week double-blind Treatment Period (dosing on Days 1 to 91; end-of-treatment visit Day 92), and a post-study Follow-Up period (approximately 14 days after their last dose). The total duration of the study for each participant will be up to approximately 19 weeks. Randomization

<sup>b Refer to the Dosing Table and Section 5.4.1 of the Clinical Study Protocol (CSP) for study drug administration details.

<sup>c Week indicates the duration of treatment completed prior to the visit, not the week in which the visit occurs. For example, "Week 1" visit is targeted to occur on Day8 (the first day of the 2nd week of treatment).

will be stratified by gender (male/female). Enrollment into each gender strata will be capped at 70% (i.e., neither gender may exceed 70% of total enrollment).

**Table 1:** Dosing Table

				W	eek	
Arm	Time (AM/PM)		Week 0 (D1-7)	Week 1 (D8-14)	Week 2 (D15-21)	Week 3 (D22-28)
W 757   W 922	AM	757/833 (mg)	30/100	30/100	60/100	120/100
K-757+K-833	PM	757/833 (mg)	pbo/pbo	30/100	60/100	120/100
K-757 alone	AM	757/833 (mg)	30/pbo	30/pbo	60/pbo	120/pbo
K-757 alone	PM	757/833 (mg)	pbo/pbo	30/pbo	60/pbo	120/pbo
Placebo to K-	AM	757/833 (mg)	pbo/pbo	pbo/pbo	pbo/pbo	pbo/pbo
757 and K-833	PM	757/833 (mg)	pbo/pbo	pbo/pbo	pbo/pbo	pbo/pbo

For additional titration information, see Section 5.4.1 of the CSP

Participants will return to the trial site at the times described in the study schematic and schedule of assessments (SOA) (Table 2) to complete study procedures. During two of the on-treatment weeks when participants do not return to the trial site, the site will contact the participants by phone in order to assess study medication compliance, new concomitant medication use, and adverse events (AEs).

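### The by-week GI adverse event curve gives Week 0 one day and every later week seven, so its first step is largely built in by the bin table

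*SAP*

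**What the plan says.** SAP 5.11.1.2 counts participants with any treatment-emergent GI event, and with nausea, vomiting, diarrhea and constipation; these "during each week will be summarized by week for each treatment group, respectively". The proportion is "calculated based on number of participants reached specified week during on-treatment period". The bins are set by a table: "Days from randomization for each week will follow table below". In that table Week 0 is Day 1, Week 1 is Days 2-8, Week 2 is Days 9-15, and so on to Week 15, Days 100-106. Incidence of any GI event, nausea and vomiting is also drawn as a line graph by maximum severity.

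The observation limit is in the same section: "On-treatment period for safety analyses are defined as from randomization to earlier of end of study date or last dose date +2 weeks". On the last dose, footnote f to Protocol Table 2 says "Dosing will end with the PM dose on Day 91", whereas the last column of the dosing table (Protocol Table 9) runs to Day 92. Visit 13 is scheduled for Day 105 with a window of three days either side.

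The dosing table in SAP 3.1 uses the same week labels differently: there Week 0 is Days 1-7 and Week 1 is Days 8-14.

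**The concern.** A proportion of participants with an event during an interval grows with the length of the interval. When one interval is a seventh as long as the next and both are divided by a head count, the two points do not measure the same thing. Joining them with a line invites the reader to see a trend.

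The stake is the reading of GI tolerability over time. Protocol 7.1 gives limiting GI intolerance as the reason for titration, and this graph shows week by week how often GI events occur as doses step up. A steep rise from Week 0 to Week 1 could be taken as onset after the first few doses. Because the dosing table calls Days 1-7 Week 0, a reader could also take the low first point as the result for the whole first dosing week.

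**Working it through.** **Inputs.** Bin limits and the on-treatment rule: SAP 5.11.1.2. Last dose on Day 91: Protocol Table 2, footnote f. Visit 13 on Days 102-108: Protocol Table 2. Fifty per arm and 20% dropout: Protocol 7.2 and 16.2. The readable documents give no GI event rate, so the weekly incidence *p* is an assumption, varied from 5 to 40%, with a constant daily risk. Day 1 is read as the randomization day.

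**1. Reproduce the table.** The rule Week *k* = Days max(1, 7*k* - 5) to 7*k* + 1 returns all 16 printed bins. Widths are one day for Week 0 and seven days for Weeks 1-15. The upper limits are the nominal days of the Week *k* visits, which probably explains the cuts.

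**2. Days observed in Week 15.** The on-treatment period ends at the earlier of end of study and 91 + 14 = Day 105.
- Follow-up on Day 105 or later: 105 - 100 + 1 = 6 days.
- Follow-up on Day 104, 103 or 102: 5, 4 or 3 days.
- If the last dose were on Day 92, the limit would be Day 106, and follow-up on or after Day 106 would fill the bin.

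**3. Expected plotted value.** With daily hazard *h* = -ln(1 - *p*)/7, a bin with *d* observed days plots as 1 - exp(-*h d*). For *p* = 20%, *h* = 0.2231/7 = 0.0319, so Week 0 plots as 1 - exp(-0.0319) = 3.1%.

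| True weekly incidence | Week 0 (1 day) | Rise to Week 1 | Week 15, 6 days | Week 15, 3 days |
|---|---|---|---|---|
| 5% | 0.7% | 6.8-fold | 4.3% | 2.2% |
| 10% | 1.5% | 6.7-fold | 8.6% | 4.4% |
| 20% | 3.1% | 6.4-fold | 17.4% | 9.1% |
| 30% | 5.0% | 6.0-fold | 26.3% | 14.2% |
| 40% | 7.0% | 5.7-fold | 35.5% | 19.7% |

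At 20%, an arm of 50 expects 1.6 participants at Week 0 and 10 at Week 1. At Week 15, with 40 completers, the six-day bin expects 7 instead of 8. Averaged over follow-up on each of Days 102 to 108, a true 20% plots as 15.1%.

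**4. Simulation.** With 50 per arm, 20% stopping early, follow-up uniform over Days 102-108 and a constant 20% per week, Week 0 is 0.032, Weeks 1-14 are 0.198 to 0.201, and Week 15 is 0.152. Part-weeks of early stoppers move the middle bins by less than 0.3 points.

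**5. If ongoing events also count.** The SAP does not say whether only new onsets count. With mean durations of 3 to 7 days, and *h* rescaled so that a mid-study bin is still 20%, Week 0 is 1.7 to 2.5% and a six-day Week 15 is 18.0 to 18.6%. The direction is the same and the end effect is smaller.

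**The case against.** The strongest defence is that the table is open about its cuts. The documents define a week as treatment completed before the visit, so Week *k* ends on Day 7*k* + 1 and Week 0 is the first-dose day. The figure shells are in a separate document (SAP 11) and may label this clearly. That convention suits a measurement taken at a visit, however, not a count of events over an interval. A label would disclose the unequal length without removing it.

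Several stronger readings are tempting, and the documents do not support them:

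- **That this graph is the trial's evidence on onset.** SAP 5.11.1.2 also plans Kaplan-Meier curves from randomization to the first GI event, nausea, vomiting and constipation. These do not depend on the bins. They do not show recurrence or settling, and diarrhea has no curve of its own, so the graph still matters for the pattern over time.
- **That the curve must drop sharply at the end.** The usual loss is one day of seven. The 9.1% figure needs every follow-up visit on Day 102. Weeks 14 and 15 are almost wholly off drug, so a real fall is possible there too.
- **That a jump will be visible in every arm, placebo included.** This rests on a constant daily risk. At 5% per week the expected counts in an arm of 50 are about 0.4 and 2.5, a gap that chance can hide.
- **That early stoppers distort the curve.** The effect is negligible. It also depends on what *reached* means: under the visit convention, reaching Week 4 could mean reaching Day 29, the last day of its bin. That reading fails at Week 15, because Day 106 lies beyond the Day 105 limit, so the word needs defining.

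It also stands that safety analyses are descriptive, without tests, and that all arms share the same bins.

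**Conclusion.** The point holds for the time trend of this display. The one-day Week 0 bin follows directly from the table. At a constant daily risk it produces a six- to sevenfold step for weekly incidences of 10 to 30%, and only a Day 1 risk about seven times the later daily risk would level it. The Week 15 shortfall is secondary: about 17% plotted for a true 20% in the usual case, more if follow-up is early, and none if the last dose is on Day 92 with follow-up on or after Day 106. The Day 91 and Day 92 entries must be reconciled.

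The sizes rest on an assumed rate and a constant daily risk; the unequal bin lengths do not. Comparisons of arms within the same week are little affected, and no endpoint or test uses the graph. This is a minor point that is cheap to correct.

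**What to change.** In SAP 5.11.1.2, replace the week table with seven-day bins on the dosing-table weeks: Days 1-7, 8-14, ..., 99-105. That gives 15 equal bins over Days 1-105 and makes the labels agree with the dosing table. At a constant 20%, the simulated curve is then flat at about 0.20 from the first bin, with 0.18 in the last; that residue comes from follow-up visits before Day 105. For the residue, either use participant-time as the denominator or footnote the last bin as incompletely observed when follow-up falls before Day 105.

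Two alternatives are worse. Folding Day 1 into the present Week 1 leaves an eight-day first bin (22.5% plotted for a true 20%, from 1 - 0.8^(8/7)). Restricting the denominator to participants observed for the whole bin drops those who leave mid-bin, possibly because of a GI event.

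In the same edit, define *reached*, say whether ongoing events count or only onsets, state that the randomization day is Day 1 (if it were Day 0, its events would fall in no bin), and say where an on-treatment event after Day 105 goes.

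The cost is one SAP table and its figure shell, before database lock. The bins would no longer end on the visit days. No data collection, sample size or test changes.

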**Table 2: Study Schedule of Assessments**

SOA													
	Screening Period	Treatment Phase by Week											ET or Post Study F/U
Visit Number	1	2 Rand.	3	4	5	6	7 g	8	9	10	11 g	12	13
Week e	~4 Weeks	Week 0	Week 1	Week 2	Week 3	Week 4	Week 5	Week 6	Week 8	Week 10	Week 12	EoT 13	Week 15
Study Day	-28	1	8	15	22	29	36	43	57	71	85	92	105
Visit Window (days)	0	0	±2	±2	±2	±2	±3	±3	±3	±3	±3	±3	±3
Administrative													
Informed Consent	X												
Inclusion/ Exclusion a	X	X											
Med History/ Demographics	X												
Prior/Concomitant Med	X	X											X
Diet and activity counseling		X				X			X				X
Clinical Assessment													
Physical Examination	X												X
Height	X												

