**Table 2: Study Schedule of Assessments (Continued)**

SOA													
	Screening Period	Treatment Phase by Week											ET or Post Study F/U
Visit Number	1	2 Rand.	3	4	5	6	7 g	8	9	10	11 g	12	13
Week e	~4 Weeks	Week 0	Week 1	Week 2	Week 3	Week 4	Week 5	Week 6	Week 8	Week 10	Week 12	EoT 13	Week 15
Study Day	-28	1	8	15	22	29	36	43	57	71	85	92	105
Visit Window (days)	0	0	±2	±2	±2	±2	±3	±3	±3	±3	±3	±3	±3
Hepatitis Screen	X												
HIV Screen	X												
hCG Pregnancy Test/FSH Test d	X	X				X			X				X
Thyroid Stimulating Hormone Test	X												
HbA1c Test	X	X										X	
Lipase/Amylase	X	X						X				X	
AE Monitoring	X	X											X
Study Drug Administration and Compliance													
Study Drug Dispensing f		X	X	X	X	X		X	X	X			
Drug Compliance Check		X	X	X	X	X	X	X	X	X	X	X	

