### Mandatory fasted visits:

Amongst the in-person clinic visits during the Treatment Period, V2 (randomization), V6 (Day 29), V9 (Day 57) and V12 (Day 92), subjects should come to the clinic in the fasted state because body weight and fasting lipids need to be assessed in the fasted state. These fasted visits should be scheduled in the morning and the AM dose of study medication should be taken after collection of blood. Dosing should be witnessed at these visits. Other in-person visits during the Treatment Period can be in the fasted or fed state and may be scheduled without regard to timing of study medication.

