#### **13.4.3. Dosing Interruptions**

If multiple days of dosing are missed due to subject error, the participant may resume QD dosing for 3 days under PI discretion before returning to the BID regimen. If less than 2 days (4 consecutive doses) are missed, the subjects should resume the BID regimen.

If study medication is missed for  $\geq 7$  consecutive days, for any reason, the decision to resume should be based on discussion between the PI and Sponsor Clinical Director.

All dosing interruptions should be documented in the case report forms.

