- f Titration will occur according to Table 9. On trial site visit days when laboratory safety tests are collected, participants will fast overnight and prior to study drug administration. Dosing will end with the PM dose on Day 91.

  § Telephone calls at Visits 7 and 11 (Day 85) to confirm drug compliance, assess AEs, and concomitant medications.

  h The optional genetic sample may be collected at any time during the study.

  Abbreviations: EoT = end of treatment, ET = end of trial; FU = follow up; hCG = human chorionic gonadotropin

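### Do the by-week GI adverse event bins need re-cutting because Weeks 1 to 3 each straddle a titration step?

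*SAP*

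**What the plan says.** SAP 5.11.1.2 counts, per week and per arm, participants with any treatment-emergent GI event, nausea, vomiting, diarrhea or constipation. It adds a line graph by maximum severity for any GI event, nausea and vomiting. The rule is "Days from randomization for each week will follow table below", under a column headed "Days from Randomization of when experiencing AE". Week 0 is Day 1, Week 1 is Days 2–8, Week 2 is Days 9–15, Week 3 is Days 16–22, and so on to Week 15 at Days 100–106.

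SAP Table 1 numbers the dosing weeks differently: Week 0 is Days 1–7, Week 1 is Days 8–14, Week 2 is Days 15–21 and Week 3 is Days 22–28. Protocol Table 9 has the same change days. In both active arms only the evening dose changes on Day 8; on Days 15 and 22 both doses change.

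For visits, note c to SAP Figure 1 says "Week indicates the duration of treatment completed prior to the visit, not the week in which the visit occurs". The Week n visit is therefore planned for Day 7n + 1.

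SAP 5.11 plans no formal testing of safety data. SAP sections 10 and 11 leave programming specifications and table shells to separate documents.

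**The concern.** K-757 is titrated to limit GI intolerance, so a reader may lay the weekly GI graph over the titration steps. Three features get in the way.

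- AE Weeks 1 to 3 in the active arms each mix two planned regimens.
- The same week label names different days in two tables of the same SAP, with one shared day per label (Days 1, 8, 15 and 22 for Weeks 0 to 3).
- The SAP does not say whether a participant counts in the week an event starts or in every week it is present. Counted by onset, an event starting on Day 15 or 22 appears only with the lower step.

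The SAP's windows for hemodynamic data (section 5.1.6) use a third set of cuts: Days 2–11, 12–18 and 19–25. If the bins blurred the link between dose step and intolerance, the description of tolerability, which is part of a secondary objective, would be less clear.

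**Working it through.** **1. Reproduce the bins.** For n = 1 to 15 the SAP rows follow Day 7(n − 1) + 2 to Day 7n + 1. For n = 1 this gives 2–8, for n = 3 it gives 16–22, and for n = 15 it gives 100–106. All rows match, and each bin ends on the nominal Week n visit day.

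**2. Map planned days to regimens (active arms).**

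| AE week | Days | Earlier regimen | Next regimen |
|---|---|---|---|
| 1 | 2–8 | 6 (Days 2–7) | 1 (Day 8) |
| 2 | 9–15 | 6 (Days 9–14) | 1 (Day 15) |
| 3 | 16–22 | 6 (Days 16–21) | 1 (Day 22) |

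Weeks 4 to 12 hold one regimen each. Week 13 (Days 86–92) holds six dosing days plus Day 92, because "Dosing will end with the PM dose on Day 91". So 3 of 16 bins are mixed, in 2 of 3 arms. This takes Day 1 as the day of randomization and first dose, as the schedule of assessments does. Read as elapsed days, the split would be 5 + 2.

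**3. Would cuts at Days 8, 15 and 22 fit better?** Whole days are too coarse, so use hours. Protocol 13.4.1 puts the morning dose at hour a, between 6 and 10 AM, and the evening dose about 10 hours later. Assume steps on the planned day, with the new regimen starting at the evening dose on Day 8 and at the morning dose on Days 15 and 22. Misplaced hours over the three boundaries are:

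- SAP bins (step day grouped with the earlier regimen): (14 − a) + 2(24 − a) = 62 − 3a
- Re-cut bins (step day grouped with the next regimen): (10 + a) + 2a = 10 + 3a

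| Morning dose | SAP bins (h) | Re-cut (h) |
|---|---|---|
| 6 AM | 44 | 28 |
| 8 AM | 38 | 34 |
| 10 AM | 32 | 40 |

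The two are equal when 62 − 3a = 10 + 3a, so a = 52/6 = 8.67, about 8:40 AM. Three seven-day bins hold 21 × 24 = 504 hours. The SAP bins misplace 32/504 to 44/504 (6% to 9%); the re-cut misplaces 28/504 to 40/504 (6% to 8%). On Day 8 alone the earlier regimen is in force until 4 to 8 PM, which is 16 to 20 of 24 hours, so there the SAP bin fits better.

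**4. Vary the step time.** The schedule shows "Study Drug Dispensing" at Visits 3, 4 and 5. Protocol 9.2 says in-person visits outside the mandatory fasted ones "may be scheduled without regard to timing of study medication". If the morning dose on Days 15 and 22 came from the old supply, all three steps would start in the evening. The SAP bins would then misplace 3(14 − a) = 42 − 3a, or 12 to 24 hours, and the re-cut 3(10 + a) = 30 + 3a, or 48 to 60 hours. The documents do not settle which dose comes first: a footnote to the schedule asks for fasting before dosing on days with safety laboratory tests, and liver tests fall at these visits.

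**5. Vary the step day.** Visits 3 to 5 have ±2-day windows. For a morning step one day late, the SAP bins misplace a hours (6 to 10) at that boundary and the re-cut 24 + a (30 to 34). One day early, the figures are 48 − a (38 to 42) and 24 − a (14 to 18). After missed days of dosing, "the participant may resume QD dosing for 3 days under PI discretion before returning to the BID regimen", so no fixed calendar bin follows the actual regimen for everyone.

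**6. The hemodynamic windows set no standard here.** SAP 5.1.6 uses them to place unscheduled, end-of-treatment and follow-up measurements, and states that other safety measures are not windowed.

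**The case for a change.** The strongest case for acting is that the plan itself ties GI tolerability to the steps. Protocol 5.3 justifies the weekly early visits partly by the wish to assess tolerability at each stage of titration. A weekly severity graph will be read in that light, and a rise that begins on a step day may show one bin early. Nor can a reader take the pooled day back out of the display. The SAP is also explicit about start dates for its time-to-first-GI-event curves but silent for the weekly counts, and the two counting rules give different totals for any event that crosses a bin boundary.

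Part of this stands. The labels do differ between the two tables, and the counting rule is unstated. A footnote giving the planned regimen for each bin and a line on onset or presence would help the reader. Both are details that table shells and programming specifications normally carry, and those documents were not available here. Either counting rule would apply alike to all arms. If events are counted by presence, one that runs past the step day also enters the next bin, so only events confined to the step day are affected.

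The case for new cuts does not stand. The SAP promises no analysis by titration step, and working steps 3 to 5 show that which cuts fit better turns on dose time and visit timing. Day-level information is available elsewhere in the plan: Kaplan-Meier curves to first GI event, nausea, vomiting and constipation, by-subject listings of adverse events, and a possible swimmer plot.

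**Conclusion.** No change to the plan is needed. The mismatch is real but small: one planned step day in each of 3 of 16 bins, in the two active arms, amounting to 32 to 44 of 504 hours if steps fall on plan. Bins that end on visit days and bins that start on step days are a fair trade-off. Re-cutting gains up to 16 hours (44 − 28) for a 6 AM dose and loses 8 (40 − 32) for a 10 AM dose, and it loses more if steps are late or begin with the evening dose. Both tables print their day ranges, so the shared labels need not mislead. The missing onset-or-presence rule is a gap that analysts can fill with a footnote.

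Between-arm contrasts within a bin, overall incidence, the Kaplan-Meier analyses and all inference are unaffected. The conclusion assumes that Day 1 is the day of randomization and first dose, and that dose times follow Protocol 13.4.1. The documents give neither GI event rates by day nor the distribution of actual step days, so the number of participants whose events would move between bins cannot be computed.
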